6.1.1.2 STUDY-SPECIFIC MANIPULATIONS

6.1.1.2.1 STUDY 1 (ASSIST VS. NO ASSIST)

Study 1 compares ASSIST to No-ASSIST. Procedures, dosage and target selection are as above (see **Section 6.1.2.1.3, ASSIST Procedures, The “How” of ASSIST**).

6.1.1.2.2 STUDY 2 (SIMPLE ASSIST VS. COMPLEX ASSIST)

Study 2 compares Simple vs. Complex ASSIST. Procedures, dosage, and target selection are as above. The experimental manipulation for complexity involves *frame* complexity: In Simple ASSIST, Index of Phonetic Complexity (IPC) of frames range from 0 to 2, whereas in Complex ASSIST, frame IPC values range from 3 to 5.

6.1.1.2.3 STUDY 3 (WORD ASSIST VS. NONWORD ASSIST)

Study 3 compares Word vs. Nonword ASSIST. Procedures and dosage are as above. The experimental manipulation for lexicality involves whether targets are words or nonwords. Target selection is the same as above except that for each individual word target, a nonword counterpart is created by changing one stressed vowel and 0 or more other sounds in the real words. Thus, all participants have 60 items (30 words, 30 nonwords), and are allocated randomly to receive ASSIST either for real word targets or for nonword targets. Nonwords are embedded in real-word frames (same as the words) and are paired with made-up creatures as referents for elicitation and pragmatics.

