2.2 BACKGROUND

Childhood apraxia of speech (CAS) is a pediatric motor speech disorder that impairs the planning of movements needed for intelligible speech. CAS may limit literacy, academic and economic outcomes and participation in society. Prevalence of CAS is estimated at 1 to 13 per 1,000 children. With ~40 million children under 10 in the US, these estimates translate to between 40,000 and 520,000 children with CAS. Over 60% of school-based speech-language pathologists report having children with CAS on their caseload, with on average 3 children per caseload. Children with CAS often show little or slow progress in standard therapy, which has led to recommendations for intensive intervention and calls for systematic research to optimize outcomes. Given the limited resources in clinical settings, it is imperative to maximize impact of these limited resources for children with CAS. Various treatments for CAS exist, with integral stimulation treatments having received the most replicated support to date. Integral stimulation treatments involve multimodal input supports to elicit speech targets (“watch me, listen to me, say what I say”). Any treatment for CAS must specify both the *what* and the *how*. The *what* relates to which targets are being practiced (sounds, syllables, words, phrases, etc.) The *how* relates to the treatment techniques and procedures applied to those targets (e.g., feedback, cues, order in which targets are practiced). This trial addresses both of these core questions in treatment for CAS.

The current evidence base for CAS treatment is limited in that it leaves several critical clinical questions unanswered. First, the efficacy of treatment has only been addressed using single-case experimental designs with relatively small samples sizes. Second, treatment targets vary in complexity across studies, which likely influenced the treatment response. Third, all integral stimulation treatment studies used real word targets but reported little to no generalization to untrained words; in contrast, other approaches targeting nonwords show generalization to untrained words. Fourth, treatment intensity has varied widely across integral stimulation treatment studies, so that optimal intensity remains unknown. Finally, outcome measures have exclusively focused on impairment (speech accuracy), not on more functional outcomes (e.g., intelligibility, participation).

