6.1.1.1.3 ASSIST PROCEDURES

ASSIST, an integral stimulation-based CAS treatment based on clinical insights and principles of motor learning (Maas et al., 2008; Schmidt et al., 2018) and neuroplasticity (Kleim & Jones, 2008; Ludlow et al., 2008) (**Table 1**), targets speech accuracy with systematic, adaptive practice on meaningful targets (words and phrases). ASSIST shares features with other motor-based CAS treatments but differs in its specific operationalization of target selection (the “what”) and systematic adaptive practice (the “how”).

Table 1. Principles of neuroplasticity and motor learning in ASSIST. FB = feedback; KR = knowledge of results; KP = of performance.

Principle	Pre-Practice	Practice
Salience	Functionally relevant targets	
Amount	16 hrs of ASSIST; 4 utterances/session	
Attention	Focus on sound & movement	
Variability	Targets embedded in 3 different frames	
	Constant prosody	Variable prosody
Schedule	Blocked	Random
Main FB type	KP	KR
FB timing	Immediate	Delayed (2-3 sec.)
FB frequency	100%	Reduced (fading)

The “What” of ASSIST. Children practice *targets* embedded in different *frames*. Targets: Each child has a set of 30 words/phrases that are *personally meaningful* (to boost motivation and carryover potential) and *within the child’s optimal challenge range*²⁴¹ (to boost motivation and expectancies through success and increase task attention by minimizing frustration) based on phonetic inventory and baseline accuracy. For Study 3 (Lexicality), we also create 30 corresponding *nonwords* by changing a stressed

vowel (and 0+ other sounds), maintaining stress and complexity (e.g., *banana – banoono*). In any session, children practice only 4 targets to maximize practice amount for those targets. **Frames:** Targets are embedded in 3 *frames* (target + frame = *utterance*) to bolster communicative relevance, practice variability, sequencing/prosodic skills, and engage language to boost a weak link between language and speech motor planning (Shriberg et al., 2012). Frames are real words (*hi mom*) or sounds (*mommy*), designed to be functional and achievable, and differ in complexity (Jakielski, 2016) to create systematic step-up/down options.

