8.1.2 DATA COLLECTION & STUDY ENDPOINTS

Data is collected by trained Data Collectors blinded to a child's treatment status, condition, and targets.

Primary efficacy outcome endpoint:

- Perceptual accuracy of treated items, judged by blinded research assistants from audio recordings. Children repeat a list of words and nonwords after a pre-recorded model (played over speakers). These speech samples serve as the basis for the primary outcome measure. Three Data Analysts (different from Data Collectors) use the three-way perceptual scoring system (e.g., Maas et al., 2012; Strand et al., 2006) to score accuracy of children's productions. Data Analysts are blinded to a child's treatment status, condition, and targets. The three-way scoring system assigns 2 points for completely correct responses, 1 point for responses with one minor error (operationally defined), and 0 points for a major error (operationally defined) or multiple errors. Scoring reliability is assessed using intra-class correlations (ICC) (single-rater two-way random effects model for absolute agreement; Hallgren, 2012; Koo & Li, 2016). Mean across analysts will be used in analysis.

Secondary efficacy outcome endpoints:

- (SE-1) Perceptual accuracy of the full 30-item set of potential targets, judged by blinded data analysts from audio recordings. Children repeat a list of words and nonwords after a prerecorded model (played over speakers). These speech samples serve as the basis for this outcome measure. Three Data Analysts (different from Data Collectors) use the three-way perceptual scoring system (e.g., Maas et al., 2012; Strand et al., 2006) to score accuracy of children's productions. Data Analysts are blinded to a child's treatment status, condition, and targets. The three-way scoring system assigns 2 points for completely correct responses, 1 point for responses with one minor error (operationally defined), and 0 points for a major error or multiple errors. Scoring reliability is assessed using intra-class correlations (ICC) (single-rater two-way random effects model for absolute agreement; Hallgren, 2012; Koo & Li, 2016). Mean across analysts will be used in analysis.

- (SE-2) ICS: Parent rating of their child's intelligibility in context, using the Intelligibility in Context Scale (ICS; McLeod et al., 2012, 2015). The ICS is completed by the same parent at each time point to control for differences between parents' perspectives.

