9.1.5 STUDY ENDPOINTS (FOR STUDIES 1-4)

Primary Endpoint

- **Primary Endpoint:** Perceptual speech accuracy of treated targets at 1 week post treatment. Improved speech motor planning skill is expected to improve speech accuracy.

Secondary Endpoints

- **Secondary Endpoint 1 (SE-1):** Perceptual speech accuracy of full 30-item target set at 1 week post treatment. Improved speech motor planning skill is expected to improve speech accuracy.
- **Secondary Endpoint 2 (SE-2):** Intelligibility-in-Context Scale (ICS; McLeod et al., 2012) mean total score at 1 week post treatment. Improved speech accuracy and speech motor planning skill are expected to improve intelligibility in the child's everyday life, as reflected in the caregiver-reported ICS.
- **Secondary Endpoint 3 (SE-3):** Focus on Outcomes of Children Under Six (FOCUS-34) (Thomas-Stonell et al., 2012) mean total score at 1 week post treatment. Improved speech accuracy and speech motor planning skill are expected to improve intelligibility and communicative confidence, which together are expected to improve communicative participation, as reflected in the caregiver-reported FOCUS-34.
- **Secondary Endpoint 4 (SE-4):** Mean percentage intelligibility based on the Test of Children's Speech (TOCS+) (Hodge et al., 2009, 2012, 2014a,b) at 1 week post treatment. Improved speech motor planning skill and accuracy are expected to improve intelligibility, as reflected in TOCS+ intelligibility.

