9.4.2 ANALYSIS OF THE PRIMARY ENDPOINT(S)

The primary endpoint measure is change score from 1 week pre to 1 week post treatment for the populations described above in **Section 9.3, Populations for Analyses**. For perceptual accuracy, at least two independent data analysts (blinded to timepoint, treatment status, condition, and targets) score each target on an ordinal 3-point scale. Mean across the data analysts for each target is then used to compute the mean across treated targets (primary endpoint) and across the full 30-item target set (secondary endpoint 1) for each timepoint (T1, T2, T3). Means are converted to percentage accuracy by dividing means by 2. Finally, difference scores are then computed by subtracting the relevant pre-treatment timepoint from the relevant post-treatment timepoint. These change scores are the primary endpoint variable entered into the analyses described below and will be reported as means with standard error.

To address the effect of ASSIST (the *ASSIST Hypothesis*, Study 1), independent two-sample t-tests will be used to compare change scores (T2 – T1) between the Immediate ASSIST group and the No ASSIST delayed control group (combined sample across Cycles 1 and 2). A separate linear model will be fitted by adjusting for potential effect of study (Cycle 1/Cycle 2) to re-assess the initial efficacy of ASSIST.

To address the effect of complexity (*Simplicity vs. Complexity Hypothesis*, Study 2), independent two-sample t-tests will be used to compare change scores between conditions (i.e., Simple/Complex). Change scores will be based on T2 – T1 for the Immediate ASSIST group and T3 – T2 for the Delayed ASSIST group. Separate linear models will be fitted by adjusting for potential effect of ASSIST delivery time (Immediate/Delayed) to re-assess the effect of complexity.

To address the effect of lexicity (*Word vs. Nonword Hypothesis*, Study 3), independent two-sample t-tests will be used to compare change scores between conditions (i.e., Word/Nonword). Change scores will be based on T2 – T1 for the Immediate ASSIST group and T3 – T2 for the Delayed ASSIST group. Separate linear models will be fitted by adjusting for potential effect of ASSIST delivery time (Immediate/Delayed) to re-assess the effect of lexicity.

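### In Study 3 the Word arm is scored on words and the Nonword arm on nonwords, so the primary t-test alone cannot separate practice condition from item-type differences in gain

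*Protocol*

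**What the plan says.** - **Manipulation.** Protocol Section 6.1.1.2.3: "The experimental manipulation for lexicality involves whether targets are words or nonwords". Each child has both kinds of item: "all participants have 60 items (30 words, 30 nonwords), and are allocated randomly to receive ASSIST either for real word targets" or for the nonword counterparts. Section 6.1.1.1.3 says the nonwords keep the stress pattern and complexity of the words.
- **Primary endpoint, Studies 1-4.** Section 9.1.5: "Perceptual speech accuracy of treated targets at 1 week post treatment". Section 9.4.2 says the rater mean for each item "is then used to compute the mean across treated targets (primary endpoint) and across the full 30-item target set (secondary endpoint 1").
- **Test.** Section 9.4.2: "independent two-sample t-tests will be used to compare change scores between conditions (i.e., Word/Nonword"). A further linear model adjusts for Immediate or Delayed delivery. The SAP's Aim 2b analysis matches.
- **Elicitation.** Section 8.1.2: "Children repeat a list of words and nonwords after a pre-recorded model (played over speakers").
- **Other outcomes.** SE-1 is accuracy over a 30-item set. The SAP instead names generalization items and does not define them. ICS, FOCUS-34 and TOCS+ are the same instruments in both arms, but they are secondary, and Section 9.2 says no power was estimated for secondary outcomes.
- **Use of the result.** Section 4.1.3.4 lets the outcomes of Studies 2 and 3 set the complexity and lexicality used in Study 4.

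**The concern.** No single sentence states how each Study 3 arm is scored, but the sections allow only one reading: the treated targets are words in one arm and nonwords in the other. In the primary score, arm and item type therefore coincide exactly. No covariate for item type can be fitted, and neither document offers another way to separate the two.

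Randomization balances the children. It does not make the two sets of items equally able to show gain. Words and nonwords may differ in headroom, in novelty, or in how much they improve from being repeated at successive visits. Any such difference goes straight into the arm contrast.

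The stake is the reading of Study 3 and the lexicality carried into Study 4. Study 1's arm comparison is not at issue. Study 2 varies the frames and Study 4 the schedule, so neither has this feature.

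**Working it through.** **1. The plan's own figure.** Inputs from Section 9.2: n = 10 per condition, d = 1.325, two-sided alpha 0.05, two-sample t-test. Power comes from the noncentral t distribution with df = 2n − 2 = 18 and noncentrality d × √(n/2) = 1.325 × √5 = 2.96. The result is 80.0%. For n = 9, 8, 7, 6 and 5 the same formula gives 75.1, 69.3, 62.5, 54.5 and 45.4%, against 75, 69, 62, 54 and 45% in Table 3. The power statement reproduces and is not in dispute.

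**2. What the primary contrast contains.** Write the mean gains as four cells, arm first and item type second: Ww, Wn, Nw, Nn.
- Primary contrast: Ww − Nn.
- Condition effect averaged over item types: C = [(Ww − Nw) + (Wn − Nn)] / 2.
- Item-type effect averaged over arms: I = [(Ww + Nw) − (Wn + Nn)] / 2.
- Sum: C + I = (2Ww − 2Nn) / 2 = Ww − Nn.

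The primary contrast is therefore exactly C + I, and the two cells it uses cannot split the sum. I is not purely nuisance: if words respond better to being trained, that also enters I.

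**3. What the other two cells add.** The word-set contrast is Ww − Nw and the nonword-set contrast is Wn − Nn. Each compares trained with untrained items, in opposite directions. Their average is C, which is the arm difference on all 60 items. Their difference, (Ww + Nn) − (Nw + Wn), is trained minus untrained and is the condition-by-item-type term.

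**4. What the existing controls remove.** Matching on stress and complexity limits differences in difficulty. Subtracting the pre-treatment score removes a constant difference in level. Neither removes a difference in gain, which is what I measures.

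**5. Illustrative size.** The documents give no value for an item-type effect, so b, in SD of the change score, is assumed. With no true training effect, the t-test rejects with the power it has at d = b and n = 10 (noncentrality b × √5):
- b = 0: 5.0%
- b = 0.25: 8.3%
- b = 0.5: 18.5%

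If b opposes a true effect of 1.325, power is computed at 1.325 − b: 62.3% for b = 0.25 and 41.5% for b = 0.5, instead of 80%.

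**The case against.** The strongest reply is that item type is the randomized manipulation. The hypotheses in Sections 4.1.3.3 and 9.1.3 ask whether children learn more effectively with words or with nonwords, and gain on trained material is a legitimate answer. Practice of real words outside sessions is a named mechanism of the Word Hypothesis, so gain by that route belongs to the effect. This stands, and it is why the primary endpoint should be kept. What it does not supply is a way to tell better learning from items that show gain more readily.

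Four stronger readings are tempting, and the documents do not support them.
- **Regression to the mean.** Targets are chosen partly "based on phonetic inventory and baseline accuracy", so a reader might expect the words to regress and bias the comparison. But Sections 4.1.2.1 and 6.3 (item 11) have target sets made before randomization, and Section 1.3 puts randomization before T1. Scored change starts at T1 or T2, so regression due to selection falls mostly before the scored interval.
- **Real words as the only primary.** This would compare trained items in the Word arm with untrained items in the Nonword arm and so favour the Word arm. It would also leave the treated-target measure on which Section 9.2 bases 1.325 SD.
- **Generalization as Study 3's stated purpose.** Section 2.2 does observe that "all integral stimulation treatment studies used real word targets but reported little to no generalization to untrained words". That is general background. The lexicality rationale in Section 2.2.3 rests mainly on motivation, outside practice and the assembly of motor plans.
- **SE-1 as equally affected.** The text does not say which 30 items apply in Study 3. That is a gap in specification, not a demonstrated fault.

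ICS, FOCUS-34 and TOCS+ are common yardsticks, but they measure more distal outcomes and carry no power estimate.

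**Conclusion.** The point holds as a limit on interpretation and a gap in specification. Study 3's primary t-test compares learning of trained words with learning of trained nonwords. It estimates the condition effect plus the item-type effect, and the plan defines no accuracy score on common items that would separate them.

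A reader might infer that the Study 3 comparison is invalid or known to be biased. The documents do not show that: they give neither size nor direction for an item-type effect. The rise in the rejection rate to about 8-19% rests wholly on the assumed 0.25-0.5 SD and on there being no true training effect.

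Study 3 serves a secondary objective, and Section 9.2 says the trial is not powered for a definitive effect. The change is still worth making because it is cheap and because the result feeds Study 4.

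**What to change.** In Protocol Sections 9.1.5 and 9.4.2 and in the SAP:
- Keep gain on treated targets as the Study 3 primary endpoint and describe it as learning of trained material.
- Define SE-1 for Study 3 on all 60 items in both arms, and define the SAP's generalization items or remove the term.
- Prespecify the word set and the nonword set, each scored in both arms, in a model with item type as a within-child factor and a condition-by-item-type term.
- State that the Study 3 conclusion, and the choice of lexicality for Study 4, rest on these results together with the treated-item result.

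**Cost.** No new data are needed if the probe already elicits all 60 items. Section 8.1.2 says only that it contains words and nonwords, so this should be confirmed. Sample size and the primary test stay as they are.

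The price is extra secondary comparisons at n = 10 per arm. If the two sets were tested formally at 0.025 each, power at 1.325 SD would be 69.6%, and the effect detectable with 80% power would rise from 1.325 to 1.484 SD. Effects on full sets may also be smaller than on treated targets, because Section 6.1.1.1.3 has only four targets practised per session and adds new ones on mastery. Each single-set comparison sets trained against untrained items, so the two must be read together.

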6.1.1.2.4 STUDY 4 (MASSED ASSIST VS. DISTRIBUTED ASSIST)

Study 4 compares Massed vs. Distributed ASSIST. Procedures and target selection are as above. Dosage is as above for the Massed ASSIST group. For the Distributed ASSIST group, intervention is delivered 1 hour per day (two 30-minute sessions), 4 days per week for 4 weeks (16 total hours of ASSIST).

6.2 FIDELITY

6.2.1 INTERVENTIONIST TRAINING AND TRACKING

Treatment fidelity is facilitated by: (a) a manualized protocol, (b) extensive training including video review and role play on the ASSIST protocol, (c) “hard-coding” decisions on tracking sheets, and (d) direct observation and joint (team) decision-making at daily debriefs. (e) Independent analysts review randomly selected treatment sessions for adherence to protocol. Each SLP provides intervention in both conditions per study to control for possible provider confounds on condition effects.

- (a) A manualized protocol (Clinician Manual) specifies the rationale, principles, targets, and techniques and procedures of ASSIST.
- (b) Training involves approximately 15 hours of group-based in-person introduction and understanding of ASSIST, including CAS and treatment rationale and structure. Procedures are illustrated with video examples, and all aspects of ASSIST are practiced to familiarity through role plays (e.g., multimodal cueing, providing different types of feedback, pre-practice procedures, practice procedures, stepping up and down based on performance).

- (c) In-session decisions are “hard-coded” on session tracking sheets. These decisions include randomized order of presentation, whether to step up or down an elicitation level, provide feedback, and elicit additional attempts, and when to take a break. The tracking sheet also contains The tracking sheet also informs between-session decisions about changing targets and frames.
- (d) Supervisors observe sessions in real time and can intervene and provide feedback regarding protocol fidelity. In addition, end-of-day debriefs during camp will include review of fidelity concerns for immediate correction and consistency across SLPs.
- (e) Independent analysts review randomly selected treatment sessions from each child for adherence to the intervention protocol, based on video review. Factors considered are those related to critical ingredients and intervention dosage.

- (5) We use blinded statistical analysis. [name] (biostatistician) does not know group (Immediate or Delayed) or condition status (Simple/Complex, Word/Nonword, Massed/Distributed) and does not interact with the children or families. There is no planned unblinding of the statistician until after completion of final analysis. Inadvertent unblinding is logged.
- (6) We use blinded camp staff. Camp staff is blinded to a child's condition and targets (blinding to phase is not possible as camp staff is responsible for bringing children to and from their individual sessions). There is no planned unblinding of camp staff. Inadvertent unblinding is logged.
- (7) We adopt equipoise in all communication about the study, including in lab meetings, training of research personnel (including treating SLPs), and interactions with children and parents. For each study, we present both conditions as potentially beneficial, never referring to any condition as "no treatment" or "optimal treatment". They will simply be referred to by their condition (e.g., Simple vs. Complex, Individual vs. Group activities). This will minimize potential bias on the part of SLPs, children, and parents (who complete ratings of intelligibility and communicative participation).
- (8) Parents are not informed of their child's assigned phase (Immediate or Delayed), condition (Simple/Complex, Word/Nonword, Massed/Distributed), or targets, to minimize placebo effects on caregiver-reported outcome measures. Parents do not observe treatment sessions and are thus not aware of which items are being treated. Parents may discover this information from their children. Follow final data collection (T3), families report whether they knew their child's phase and condition, and are informed of the actual allocation. Inadvertent unblinding is logged.
- (9) We use the same clinicians across conditions in each recruitment cycle to control for clinician confounds. Each clinician will treat an equal number of children in each condition.
- (10) Treatment fidelity will be facilitated by a manualized protocol, extensive training including video review and role play, "hard-coding" in-session decision on session tracking sheets, and real-time observation and daily team debrief discussions (see **Section 6.2, Fidelity**). Independent research assistants also review randomly selected videos of treatment sessions for adherence to protocol.
- (11) We create target sets before randomization to avoid bias.
- (12) We use pre-recorded auditory models to elicit primary outcome data samples (imitation of individualized target words and phrases). This controls for any differences between or within data collectors in terms of dialect or speaking style, which may affect how a child says a target.
- (13) Outcome data collection occurs in a different room from the room where a child received treatment in order to avoid possible inflation of effects due to contextual cue effects.
- (14) Diagnosis of CAS is rigorous in that it is based on *both* a rigorous clinical SLP expert criterion (see 15 below) *and* the Maximum Performance Task protocol (Thoonen et al. 1996, 1999), the only prospectively validated tool with strong diagnostic accuracy for CAS.
- (15) We use an operationalized criterion of CAS clinical diagnosis based on clinical expert judgment from three independent recognized expert SLPs (CAS3SLP score > 1).

